7.2 NULL AND ALTERNATIVE HYPOTHESES

No formal hypothesis testing is planned in this trial. All analyses in this trial are descriptive and exploratory in nature.

7.3 PLANNED ANALYSES

Analysis of efficacy and safety will be based on the treated set, which will consist of all patients who receive at least one dose of BI 905711.

For the determination of the MTD, only DLT evaluable patients will be considered. Patients will be analyzed according to their starting doses. Any other analysis sets will be defined in the TSAP. No per protocol set will be used in the analysis. However, important protocol violations will be summarised. The TSAP will specify the important protocol violations in detail.

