FLOW CHART: PHASE IA (CONT.) – No longer applicable per CTP v7.0

FLOW CHART: PHAN	SE IA (C	 	 	0 101	iger a	ррпс		-										
							Tre	eatment	Perio	od						Post-Treatmen	t	
Visit	Screen		Cyclo	e 1*		Cycl *ß	e 2	C	ycle (3 *β		Cycle	4 *β	Cycle 5 and beyond * _β	EOT**	EOR ***	FU for PD‡	FU for survival status‡
Day	-28	1	2	3	8	1	2	1	2	3	8	1	2	1	Day 0-7 after			
(day range)	- 1	(+3)			(± 3)	(+2)		(+2)			(± 3)	(+2)		(+2)	last dose	after last dose		
Fresh tumor biopsy (optional) ¹¹	Х																	
Archival tumor tissue (mandatory) ¹²		X																
[¹⁸ F]FDG-PET/CT ¹³	x ¹³							x ¹³										
Adverse Events ¹⁴	Х	X	Х	x	Х	Х	X	X	X	Х	X	X	Х	X	Х	Х		
Concomitant Therapy	Х	х	Х	х	Х	Х	X	X	X	х	Х	Х	Х	X	X	Х		
Tumor assessment by CT/MRI RECIST 1.1 ¹⁵	x ¹⁵											x ¹⁵						
Termination of study medication															X			
Patient vital status																		Х
Brain MRI (in phase Ia only) ¹⁶	х																	

17Apr2023

Clinical Trial Protocol

Page 11 of 165

Proprietary confidential information © 2023 Boehringer Ingelheim International GmbH or one or more of its affiliated companies

- (*) Each treatment Cycle has a duration of 14 days
- (**) Patients who discontinue trial treatment prematurely should undergo the End of Treatment (EOT) visit as soon as possible. If assessments due at EOT are not completed, they may be performed at the 30-Day Safety FUP Visit.
- (***) The 30-Day Safety Follow-up visit is the End of Residual Effect Period visit (EOR) which must happen at the earliest 30 (+ 5) days after the last dose of treatment (see Section 6.2.3.2). ‡Additional follow-up visits for progression after the 30-Day safety follow-up visit will be performed for patients who discontinue for reasons other than progression or death. Follow-up continues until progression per the imaging schedule (see Section 5.1). The follow-up visits for survival status will be performed every 12 weeks (+/-7 days)(in person or by telephone) until death, lost to follow-up, withdrawal of consent, or end of the whole trial (see Section 6.2.3.3).

βFor every cycle, the interval between two dose administrations must be always at least 14 days.

¹Written informed consent must be obtained before any protocol specific screening assessments are performed. Re-consenting may become necessary when new relevant information becomes available and should be conducted according to the Sponsor's instructions. Separate consent is to be obtained for optional biomarker sampling.

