2. TRIAL OBJECTIVES AND ENDPOINTS

2.1 MAIN OBJECTIVES, PRIMARY AND SECONDARY ENDPOINTS

2.1.1 Main objectives

Phase Ia:

- Explore safety and establish the maximum tolerated dose (MTD)/recommended dose levels for phase Ib expansion phase of BI 905711 based on the frequency of patients experiencing dose limiting toxicities (DLTs) during the MTD evaluation period. The MTD evaluation period is defined as the first two treatment cycles (from first dose administration until the day preceding the third dose administration or end of REP in case of discontinuation before start of Cycle 3).
- Explore pharmacokinetics/pharmacodynamics and efficacy to guide the determination of a potentially effective dose range for phase Ib in the absence of MTD.

Phase Ib:

• Evaluate efficacy and safety of BI 905711 at a potentially effective dose range and determine the Recommended Phase 2 Dose (RP2D)

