4.1.2.3 Dose modification

Patients who experience DLT (Section 5.2.6.1.5) or any grade 3-4 AE possibly related to BI 905711 should interrupt or delay treatment until recovery to CTCAE grade 1 or baseline condition. Restart of BI 905711 treatment can be considered at reduced dose if toxicity is adequately managed and there is approval from the medical representative of Sponsor.

For phase Ia, the subsequent dose level was reduced to the next lower dose level as specified in Table 4.1.2.1: 1 after approval by the Sponsor and provided SMC has agreed the lower dose level is considered safe.

Patients on the first 3 dose levels who continued treatment after completion of Cycle 4, were considered for intra-patient dose escalation to a higher dose level that was determined as being safe and appropriate by the SMC. More than one dose-escalation was considered if deemed appropriate by the Investigator.

For phase Ib, restart of BI 905711 treatment can be considered at a reduced dose by 25% to 50%, if there is approval from the medical representative of the Sponsor.

No more than 2 dose reductions will be allowed. After a dose reduction, no dose re-escalation will be permitted.

At the time the recommended doses for expansion are determined by SMC, patients that are on any other dose levels may be adapted to the recommended dose at investigator's discretion.

Page 63 of 165

Proprietary confidential information © 2023 Boehringer Ingelheim International GmbH or one or more of its affiliated companies

The dose cannot be escalated if the dose has been previously reduced for toxicity reason.

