7.8.1 Adverse events

Adverse events will be coded using the Medical Dictionary for Drug Regulatory Activities (MedDRA). Standard BI summary tables and listings will be produced. All adverse events with an onset between start of treatment and end of the residual effect period (REP), a period of 35 days after the last dose of trial medication, will be assigned to the on-treatment period for evaluation.

All treated patients will be included in the safety analysis. In general, safety analyses will be descriptive in nature and will be based on BI standards. No hypothesis testing is planned.

Statistical analysis and reporting of adverse events will concentrate on treatment-emergent adverse events, i.e. all adverse events occurring between start of treatment and end of the residual effect period. Adverse events that start before first drug intake and deteriorate under treatment will also be considered as 'treatment-emergent.'

The analyses of adverse events (AE) will be descriptive in nature. All analyses of AEs will be based on the number of patients with AEs and not on the number of AEs. Frequency of patients with AEs will be tabulated by treatment dose, highest CTCAE grade, system organ class (SoC) and preferred term after coding according to the current version of MedDRA at the database lock. In addition, AEs will be tabulated by preferred terms only. The SoC will be sorted alphabetically. In tables displaying AEs by preferred terms, this will be sorted by descending frequency of AEs in the "Total" BI 905711 group.

Summary tables and listings of AEs, SAEs, related AEs, related SAEs, AEs of special interest, AEs leading to dose reduction, AEs leading to treatment discontinuation and AEs leading to deaths will be provided. In addition the number of DLTs in the MTD period and during the study will be provided.

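### Adverse events and late DLTs that arise after a planned dose-level change would be counted under the starting dose, because the SAP has no rule for patients treated at more than one level

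*Protocol*

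**What the plan says.** Protocol 4.1.2.3 describes planned changes of dose during treatment.

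- **Escalation within a patient (Phase Ia).** "Patients on the first 3 dose levels who continued treatment after completion of Cycle 4, were considered for intra-patient dose escalation". The target was a higher level that the SMC judged safe and appropriate, and more than one step was possible.
- **Move to the recommended dose.** Once the SMC has set the expansion doses, "patients that are on any other dose levels may be adapted to the recommended dose at investigator's discretion". No cycle limit is stated.
- **Reduction.** In Phase Ia this was to the next lower level; in Phase Ib it is by 25% to 50%, with at most two reductions.

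The only attribution rule visible in either document is in Protocol 7.3: "Patients will be analyzed according to their starting doses". It directly follows a sentence about MTD determination.

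SAP Table 6.1:1 defines one on-treatment period per patient, from the first administration to 35 days after the last, or to database lock for patients still on treatment. SAP 6.1 pools Phase Ia and Ib data for the main analysis. SAP 7.8.1 states: "Frequency of patients with AEs will be tabulated by treatment dose, highest CTCAE grade, system organ class (SoC) and preferred term". SAP 7.4.1 summarises DLTs over the whole treatment period at each dose level. Protocol 2.1.2 provides for re-running the BLRM after expansion with DLTs from all cycles, and Protocol 5.2.6.1.5 uses DLT-type events from all cycles in choosing the RP2D.

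**The concern.** A patient can be treated at two or more dose levels, while by-dose outputs that cover the whole treatment period allow one dose per patient. An AE that starts at 0.6 mg/kg in a patient who began at 0.2 mg/kg would count against 0.2 and be missing from 0.6.

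The lowest levels are very small: Table 4.1.2.1:1 lists one CRC and one non-CRC patient at each of the first two. One late event there is 1/1 of the CRC patients, or 1/2 of the column.

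Dose is the only covariate in the BLRM of Protocol 7.1. A late DLT entered at the starting dose is therefore an input error in that model, and it pulls the fitted dose–toxicity curve up at low doses and down at high doses.

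What is at stake is the accuracy of the by-dose safety tables in the trial report, and of any all-cycle BLRM re-run.

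**Working it through.** **1. Timing.** "The MTD evaluation period is defined as the first two treatment cycles" (Protocol 2.1.1), and "Each treatment Cycle has a duration of 14 days". The MTD window is therefore about 2 × 14 = 28 days. Escalation needs four completed cycles, 4 × 14 = 56 days, so it starts at about Day 57. The Cycle 1–2 DLT data are complete before this route opens.

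**2. How many patients could escalate.** In Table 4.1.2.1:1, levels 1–3 hold 1 + 1 + 4 = 6 CRC patients (table minimum) and up to 1 + 1 + 4 = 6 non-CRC patients, 12 in all. All eight levels hold 1 + 1 + 6 × 4 = 26 CRC and up to 26 non-CRC patients, 52 in all. The share is 12/52 = 23% by plan. Median treatment in Phase Ia was 30.5 days (range 15–246, Protocol 1.2), so most patients stopped before Day 57. The number who actually changed level is not stated.

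**3. Reproducing the plan's model.** The model is logit(p) = log(α) + β·log(d/3.6), with the three-component prior of Table 7.1:1, evaluated by importance sampling. Prior probability that the DLT rate is at least 0.33:

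| Dose (mg/kg) | 0.02 | 0.06 | 0.2 | 0.6 | 1.2 | 2.4 | 3.6 | 4.8 |
|---|---|---|---|---|---|---|---|---|
| Table 7.1:2 | 0.075 | 0.093 | 0.119 | 0.160 | 0.196 | 0.252 | 0.298 | 0.338 |
| Recomputed | 0.073 | 0.091 | 0.119 | 0.158 | 0.195 | 0.250 | 0.298 | 0.339 |

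Agreement is within 0.002. Overdose probabilities for scenarios 1, 7, 14, 18 and 20 of Table 10.3:1 agree to about 0.012.

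**4. Effect of attributing one late DLT (illustration).** None of this was observed. Assume the 48 Phase Ia patients are laid out as 1, 1, 8, 8, 8, 8, 8, 6 across the eight levels; only the groups of 8 at 0.6, 1.2 and 2.4 mg/kg come from Protocol 1.2. Assume one late DLT in a patient who started at 0.2 and was receiving 2.4 mg/kg.

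| | By starting dose | By dose at onset (patient moved) |
|---|---|---|
| Crude rate at 0.2 | 1/8 = 12.5% | 0/7 |
| Crude rate at 2.4 | 0/8 | 1/9 = 11.1% |
| Posterior mean at 0.2 | 0.017 | 0.011 |
| Posterior mean at 4.8 | 0.043 | 0.055 |
| P(rate ≥ 0.33) at 4.8 | 0.0001 | 0.0012 |

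With a 1, 1, 6, 8, 8, 8, 8, 8 layout, the posterior mean at 4.8 is 0.042 against 0.051, and P(rate ≥ 0.33) is below 0.0001 against 0.0005.

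**5. A harsher case.** With only the 26 minimum CRC patients and two such late DLTs, P(rate ≥ 0.33) at 4.8 mg/kg is 0.007 by starting dose and 0.035 by dose at onset. That is about a five-fold difference, but both values are far below the 0.25 limit.

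**The case against.** **The starting-dose sentence may apply to the MTD only.** It follows the MTD sentence, and for that analysis starting dose is right. The ambiguity is real, but on this reading no visible rule assigns AEs, later DLTs or response after a dose change, so the gap remains.

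**The rule may exist elsewhere.** SAP 6.1 sends treatment codes and labels to a separate ADS Plan and Data Guide, and some SAP sections are not visible. This stands as a limit: the point is about the documents as they can be read.

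**The documents already give partial traceability.** SAP 6.1 shows MTD-period and whole-period DLTs separately, AEs are listed by patient, and SAP 7.3 lists actual against planned dose. A reader could trace a switched patient by hand, but the by-dose tables would still be wrong for that patient.

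**Little now depends on it.** The SMC chose the expansion doses with patient-level data, development has been terminated, and all analyses are descriptive. The SAP's own BLRM in 7.4.1 uses MTD-period DLTs only, so the re-run issue arises only if the Protocol 2.1.2 re-run is carried out. All of this stands and limits the size.

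**Stronger readings the documents do not support.**

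- A reader might infer dose jumps of up to 240-fold (0.02 to 4.8 mg/kg). The target level had to be judged safe. Clearing all eight levels takes at least 8 × 28 = 224 days, plus the one-week stagger at six levels, 6 × 7 = 42 days, which makes 266 days. The longest treatment reported is 246 days.
- A reader might infer that low-dose disease control was really earned at a higher dose. Eight Phase Ia patients were progression-free at 4 months or more (3 CRC + 5 non-CRC), and 3 + 1 + 1 = 5 are placed at 0.6, 1.2 and 2.4 mg/kg. The starting doses of the other three are not given. They could be 3.6 or 4.8 mg/kg, which were not open to escalation after Cycle 4, and no switch is documented.
- A reader might infer biased Phase Ia PFS. In the visible text PFS is a Phase Ib endpoint. Phase Ia efficacy is objective response, and Protocol 1.2 describes no complete or partial response.

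**Conclusion.** The concern holds for AEs and for DLTs counted over the whole treatment period. As written, events after a dose-level change are tabulated under a dose the patient no longer received, and late DLTs would enter an all-cycle BLRM re-run at the wrong dose. The Cycle 1–2 MTD analysis is not affected by escalation after Cycle 4. In Phase Ib, grouping randomised patients by assigned dose after a reduction is a standard choice and is not faulted here.

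The practical effect is probably small: there were 0 DLTs in 48 Phase Ia patients, most were treated for less time than escalation requires, and development has ended. No dose decision changes in the illustrative runs. Those runs rest on assumed cohort sizes and assumed late DLTs. The true effect depends on how many patients switched, which the documents do not say.

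**What to change.** Keep starting dose for the MTD analysis and as the primary grouping. Then, in SAP 6.1, 7.4.1 and 7.8.1:

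1. Define treatment dose, stating whether it means starting dose or dose at onset.
2. Report how many patients changed dose level, from which level to which, and in which cycle.
3. Add supplementary AE and whole-period DLT tables by dose at onset, or a separate column for events after a dose-level change.
4. In any BLRM re-run that uses all-cycle DLTs, enter a DLT that occurs after a change at the dose received at onset.
5. Flag switched patients in the Phase Ia response displays. Do not truncate response or PFS at the change: only patients still on treatment after Cycle 4 can escalate, so truncation would selectively remove follow-up from those doing well.

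The cost is one derived variable and a few extra columns. Drug administration and dose changes are already collected in the eCRF. Switched patients will appear under two doses. Columns for escalation after Cycle 4 will contain patients selected for having tolerated at least four cycles; a footnote should say so.

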7.3.1 Primary endpoint analyses

Phase Ia: In order to determine the MTD, the number of patients with DLTs will be assessed per dose level in phase Ia. The MTD will be determined as described in Section 7.1. Patients with DLTs that occurred during the first two treatment cycles and later cycles may be tabulated separately.

For doses that will be recommended for phase Ib, totality of data will be considered including efficacy and PK. Details are described in Section 3.1.1.

Time frame: Database lock (DBL) will occur when either MTD is found or the recommended dose range for phase Ib is determined, and all the patients have had at least 2 post-baseline tumor assessment timepoints excluding patients who have discontinued earlier.

Phase Ib:

The primary endpoints in the dose-expansion part are objective response (OR) and PFS derived from the data of all cycles. The PFS will be summarized using PFS4 rate, defined as the proportion of patients with PFS >= 4 months, and will be presented descriptively. Objective response will be analyzed in terms of objective response rate (ORR), defined as the proportion of patients with best overall response of complete response (CR) or partial response (PR). For each dose level, the proportion of patients with objective response (CR and PR) will be calculated with 95% confidence interval.

The observed response rate and PFS4 rate for different dose levels will be compared to recommend the optimal dose level (RP2D). If applicable, a Bayesian hierarchical model will be used to get the adjusted response rate for each dose level, and comparisons will be made among different dose levels to make a recommendation on the optimal dose level (RP2D).

Time frame: The database lock will occur after all treated patients have had at least three post-baseline tumor assessment timepoints (unless patients discontinue the treatment early due to any reasons). A clinical trial report will follow.

Page 100 of 165

Proprietary confidential information © 2023 Boehringer Ingelheim International GmbH or one or more of its affiliated companies

7.3.2 Secondary endpoint analyses

Secondary endpoints will be analyzed by descriptive statistics. PK analyses are specified in Section 7.3.5 and Section 5.3.

Time frame: the same as the primary endpoint analyses time frame.

Details will be provided in the TSAP.

7.3.4 Safety analyses

Adverse events will be coded using the Medical Dictionary for Drug Regulatory Activities (MedDRA). Standard BI summary tables and listings will be produced. All adverse events with an onset between start of treatment and end of the REP, a period of 30 days ($+ \le 5$ days) after the last dose of trial medication, will be assigned to the on-treatment period for evaluation.

All treated patients will be included in the safety analysis. In general, safety analyses will be descriptive in nature and will be based on BI standards. No hypothesis testing is planned.

Statistical analysis and reporting of adverse events will concentrate on treatment-emergent adverse events, i.e. all adverse events occurring between start of treatment and end of the REP. Adverse events that start before first drug intake and deteriorate under treatment will also be considered as 'treatment-emergent'.

Frequency, severity, and causal relationship of adverse events will be tabulated by system organ class and preferred term after coding according to the current version of the Medical Dictionary for Drug Regulatory Activities (MedDRA) at database lock.

Laboratory data will be analyzed both quantitatively as well as qualitatively. The latter will be done via comparison of laboratory data to their reference ranges. Values outside the reference range as well as values defined as clinically relevant will be summarised. Treatment groups will be compared descriptively with regard to distribution parameters as well as with regard to frequency and percentage of patients with abnormal values or clinically relevant abnormal values.

Vital signs, physical examinations, or other safety-relevant data observed at screening, baseline, during the course of the trial and at the end-of-trial evaluation will be assessed with regard to possible changes compared to findings before start of treatment.

Page 101 of 165

Proprietary confidential information © 2023 Boehringer Ingelheim International GmbH or one or more of its affiliated companies

7.3.5 Pharmacokinetic and pharmacodynamic analyses

The PK parameters will be calculated by means of non-compartmental analysis. Descriptive statistics will be used to evaluate plasma concentration data and PK parameters. PK parameters will be calculated according to the relevant BI internal procedures. Further details on analysis will be described in the TSAP.

7.4 INTERIM ANALYSES

The Sponsor will continuously monitor the safety. The dose escalation design foresees that the Sponsor and the SMC perform regular safety evaluations. These evaluations will be unblinded.

For efficacy, in phase Ib, an arm might be terminated early due to futility if lack of efficacy signal (in terms of OR, PFS and PD-modulation) observed among evaluable patients. If any DLTs observed in patients enrolled in phase Ib, the BLRM will be run to confirm if the dose level still fulfills the overdose risk control.

No formal interim analysis is planned for PK and immunogenicity.

Preliminary, exploratory analysis of PK and if applicable of immunogenicity will be performed prior to database lock during study conduct based on all evaluable data at the time of analysis. This will be performed to support dose escalations and e.g. in case the information is needed to inform other activities during the development of substance such as concomitant treatment restrictions in other trials. In contrast to the final calculations, the preliminary, exploratory analysis will be based on planned sampling times rather than on actual times, regardless of whether actual times were within the time windows or not. Therefore, minor deviations of preliminary and final results may occur. No formal preliminary PK and immunogenicity report will be written.

7.5 HANDLING OF MISSING DATA

No imputation will be performed on missing efficacy data. Missing baseline laboratory values will be imputed by the respective values from the screening visit. No other imputations will be performed on missing data although every effort will be made to obtain complete information on all adverse events, with particular emphasis on potential DLTs.

Pharmacokinetcis:

Handling of missing PK data will be performed according to the relevant BI internal procedure.

PK parameters that cannot be reasonably calculated based on the available drug concentration-time data will not be imputed.

Page 102 of 165

Proprietary confidential information © 2023 Boehringer Ingelheim International GmbH or one or more of its affiliated companies

If the actual sampling time is not recorded or is missing for a certain time point, the planned time will generally be used for this time point instead. Pharmacokinetic parameters which cannot be determined will be identified by "not calculated" (NC).

7.6 RANDOMISATION

For phase Ib, patients will be randomised into four cohorts of BI 905711 with approximately 60 patients. BI will arrange for the randomisation and the packaging and labelling of trial medication. The randomisation list will be generated using a validated system, which involves a pseudo-random number generator so that the resulting treatment will be both reproducible and non-predictable. Access to the randomisation list will be controlled and documented.

